### **6.10.4. Clinical Laboratory Evaluation**

All relevant hematology and chemistry laboratory values will be graded according to CTCAE Version 4. These calculated grades will be summarized by cycle and maximum post-baseline grade over the entire study.

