- hematologic: absolute neutrophil count (ANC)  $\geq 1.5 \times 10^9/L$ , platelets  $\geq 100 \times 10^9/L$ , and hemoglobin  $\geq 8$  g/dL. Patients may receive erythrocyte transfusions to achieve this hemoglobin level at the discretion of the investigator; however, initial study drug treatment must not begin earlier than the day after the erythrocyte transfusion.
  - hepatic: Total bilirubin  $\leq 1.5$  times the upper limit of normal (ULN) and alanine aminotransferase (ALT) and aspartate aminotransferase (AST)  $\leq 3.0$  times ULN (or ALT and AST  $\leq 5$  times ULN if liver metastases are present).
  - renal: serum creatinine  $\leq 1.5$  times ULN.
- [7] are female and  $\geq 18$  years of age
- [8] have discontinued previous localized radiotherapy for palliative purposes or for lytic lesions at risk of fracture at least 2 weeks prior to randomization and recovered from the acute effects of therapy (until the toxicity resolves to either baseline or at least Grade 1) except for residual alopecia or peripheral neuropathy

- [9] have given written informed consent prior to any study-specific procedures
- [10] are able to swallow capsules
- [11] are reliable, willing to be available for the duration of the study, and willing to follow study procedures.

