ALT Increased (Sections 9.4.1.1.4.2. and 10.3.3.1)	Persistent or recurrent a Grade 2 (>3.0-5.0×ULN), or Grade 3 (>5.0-20.0×ULN) c	Dose MUST be suspended until toxicity resolves to baseline or Grade 1.	Dose MUST be reduced by 1 dose level.

ALT Increased (Sections 9.4.1.1.4.2 and 10.3.3.1)	Grade 4 (>20.0×ULN)	Blinded study drug MUST be discontinued.	Blinded study drug MUST be discontinued.
ALT Increased with increased total bilirubin, in the absence of cholestasis (Sections 9.4.1.1.4.2)	Grade 3 increased ALT (>5.0 × ULN) with total bilirubin >2 × ULN	Blinded study drug MUST be discontinued	Blinded study drug MUST be discontinued

Abbreviation: ALT = alanine transaminase; ASCO = American Society of Clinical Oncology.

Note: MUST = mandatory.

- a Determination of persistent events will be at the discretion of the investigator. Recurrent toxicity refers to the same event occurring within the next 8 weeks (as measured from the stop date of the preceding event). As a general guidance, based on the risk/benefit balance assessment per the investigator, for a patient who experiences a new episode of Grade 3 hematological toxicity after more than 8 weeks following the last episode of same Grade 3 hematological toxicity, the investigator may consider resuming the patient on the same drug dose should the patient satisfy the following conditions:
- shows stable hematological counts (Grade ≤2) during that timeframe
  - has absence of any signs or risk of infection
  - is benefiting from study treatment
- b Additional guidance for renal and hepatic monitoring is in Sections 10.3.3.1 and 10.3.3.2
- c Grade 3 ALT increased is a trigger for additional assessments and possibly hepatic monitoring. See Section 10.3.1.1 for additional guidance for hepatic monitoring

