#### **10.3.3.2. Renal Function**

Abemaciclib has been shown to increase serum creatinine due to inhibition of renal tubular secretion of creatinine without affecting cystatin C-calculated glomerular filtration rate. Increases in serum creatinine occurred within the first 2 weeks of treatment, remained stable through the treatment period, and were reversible upon treatment discontinuation. If deterioration of renal function is suspected, serum creatinine should not be the only measure used to assess a patient's renal function.

Dose adjustment (omission, reduction, or discontinuation) should not solely be based on interpretation of serum creatinine values because these may not reflect renal function. If deterioration of renal function is suspected per the investigator's clinical assessment, dose alteration should follow the protocol guidance for non-hematological toxicities ([Table JPBQ 9.2](#)).

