### **12.2.12. Safety Analyses**

All safety summaries and analyses will be based upon the Safety Population as defined in Section [12.2.1](#).

Overall exposure to study drug, the numbers of patients completing each cycle, and the dose intensity will be summarized using descriptive statistics. The number of patients with any dose adjustment will be presented for the entire treatment period as well as for each cycle. The number of patients with dose reductions, delays, or omissions will also be summarized, as will the reasons for dose adjustments.

Adverse events will be reported using MedDRA. Investigators will report a verbatim AE term and a CTCAE v4.0 term and severity for all AEs. For analysis purposes, the following process will be used:

- The CTCAE v4.0 term reported by the investigator will be mapped to the MedDRA Preferred Term (PT) and SOC using the corresponding MedDRA Lower Level Term (LLT), unless the reported CTCAE term is ‘Other – specify.’
- If the reported CTCAE term is ‘Other – specify,’ the MedDRA LLT, PT, and SOC centrally mapped from the verbatim AE term will be used.
- All listings and summaries will use the PT resulting from this process.

Preexisting conditions are defined as AEs that begin prior to the first dose of study drug.

A TEAE is defined as an event that first occurred or worsened in severity after baseline. Comparisons of preexisting conditions to on-treatment events at the LLT level will be used in the treatment-emergent computation.

The following summaries will be produced by PT within SOC: preexisting conditions, SAEs, TEAEs, drug-related TEAEs, and procedure-related TEAEs.

The following summaries will be produced by PT within SOC and maximum CTCAE grade: laboratory-based TEAEs, nonlaboratory-based TEAEs, drug-related laboratory-based TEAEs, and drug-related nonlaboratory-based TEAEs.

Reasons for death will be summarized separately for on-therapy and within 30 days of treatment discontinuation.

Hospitalizations and transfusions during the study treatment period or during the 30-day short-term follow-up period will be summarized by treatment group.

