#### 6.1.2. Definitions and Conventions

**Study drug** refers to abemaciclib or placebo.

**Study treatment** refers to study drug plus NSAID/fulvestrant.

The **date of randomization** is the date the patient was randomly assigned to study treatment using the interactive web response system (IWRS).

The **date of first dose** is the date of the first dose of study drug or NSAID/fulvestrant.

The **baseline value of a safety assessment** is the last value observed prior to the first dose of study drug or NSAI/fulvestrant.

The **baseline value of an efficacy assessment** is the last value observed prior to the date of randomization. If a patient's first assessment occurs after randomization but prior to the first dose, this assessment will be used as the baseline.

The **study day of a safety event or assessment** will be calculated as:

- the difference between the date of the event or assessment and the date of first dose plus 1 for all events or assessments occurring on or after the day of first dose. For example, if an event occurs on 08JUN2014 and the date of first dose was 06JUN2014, the study day of the event is 3.
- the difference between the date of the event or assessment and the date of first dose for all events or assessments occurring before the day of first dose. For example, if an event occurs on 05JUN2014 and the date of first dose was 06JUN2014, the study day of the event is -1.

The **study day of an efficacy event or assessment** will be calculated as:

- the difference between the date of the event or assessment and the date of randomization plus 1 for all events or assessments occurring on or after the date of randomization.
- the difference between the date of the event or assessment and the date of randomization for all events or assessments occurring before the date of randomization.

One **month** is defined as 365/12 days.

Unless otherwise noted, **summaries of continuous variables** will include a mean, median, standard deviation, minimum, and maximum.

Unless otherwise noted, **summaries of categorical variables** will include the frequency and percentage (relative to the population being analyzed) of each category.

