### **6.10.2. Adverse Events**

Adverse event (AE) terms and severity grades will be assigned by the investigator using Common Terminology Criteria for Adverse Events (CTCAE) Version 4. In addition, AE verbatim text will also be mapped by the sponsor or designee to corresponding terminology within MedDRA. Adverse events will be reported using the following reporting process:

- The CTCAE Version 4 term reported by the investigator will be mapped to the MedDRA PT and system organ class (SOC) of the corresponding MedDRA lower level term (LLT), unless the reported CTCAE term is 'Other – specify'.
- If the reported CTCAE term is 'Other – specify' the MedDRA LLT, PT and SOC mapped from the verbatim AE term will be used.
- All listings and summaries will use the PT resulting from this process.

Pre-existing conditions are defined as AEs that begin prior to the first dose of study drug.

A treatment emergent adverse event (TEAE) is defined as any AE that begins on or after the day of first dose or any pre-existing condition that increases in CTCAE grade on or after the day of first dose. Comparisons of pre-existing conditions to on-treatment events at the LLT level will be used in the treatment-emergent computation.

A serious adverse event (SAE) is any AE during this study that results in one of the following outcomes:

- death
- initial or prolonged inpatient hospitalization
- a life-threatening experience (that is, immediate risk of dying)
- persistent or significant disability/incapacity
- congenital anomaly/birth defect
- considered significant by the investigator for any other reason.

Important medical events that may not result in death, be life-threatening, or require hospitalization may be considered SAEs when, based on appropriate medical judgment, they may jeopardize the patient and may require medical or surgical intervention to prevent one of the outcomes listed in this definition.

AE will also be classified based on the relationship to the study treatment.

The following TEAE/SAE listings and summaries will be produced:

- Overview of TEAEs
- Summary of TEAEs by PT (all grade and grade  $\geq 3$ )
- Summary of TEAEs by SOC and PT (all grade and grade  $\geq 3$ )
- Summary of TEAEs by PT and maximum grade (1-5)
- List of SAEs
- Summary of SAEs by SOC and PT (all grade and grade  $\geq 3$ ).

The four summaries will be produced for all TEAEs/SAEs and repeated for TEAEs/SAEs related to study treatment.

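### SAP 6.10.4 summarises calculated laboratory grades without reference to the patient's own baseline grade, which inflates any-grade and low-grade rates in both arms and pulls the between-arm ratio toward 1

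*SAP*

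**What the plan says.** SAP 6.10.4 (Clinical Laboratory Evaluation) has two sentences. The first applies CTCAE Version 4 grades to the relevant hematology and chemistry values. The second sets out the output: "These calculated grades will be summarized by cycle and maximum post-baseline grade over the entire study". It names no shift table and no rule that counts only grades that have risen.

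A baseline exists elsewhere in the SAP. Under SAP 6.1.2 the baseline of a safety assessment "is the last value observed prior to the first dose of study drug or NSAI/fulvestrant". Adverse events are referred to prior status in SAP 6.10.2: "Comparisons of pre-existing conditions to on-treatment events at the LLT level will be used in the treatment-emergent computation".

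Protocol 7.1, criterion 6, admits patients with some abnormal laboratory values:
- ALT and AST may be up to 3.0 × ULN, or up to 5 "times ULN if liver metastases are present".
- Bilirubin and creatinine may each be up to 1.5 × ULN.
- Hemoglobin may be as low as 8 g/dL: "Patients may receive erythrocyte transfusions to achieve this hemoglobin level at the discretion of the investigator".

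Protocol Table JPBQ.9.2 gives the ALT grade limits: "Grade 2 (>3.0-5.0×ULN), or Grade 3 (>5.0-20.0×ULN".

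Protocol 12.2.12 also plans adverse event tables for laboratory events: "The following summaries will be produced by PT within SOC and maximum CTCAE grade: laboratory-based TEAEs, nonlaboratory-based TEAEs". Both documents define a treatment-emergent event as one that is new or has worsened since baseline.

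**The concern.** A patient with liver metastases may enter with ALT at 4 × ULN, which is Grade 2. If she stays there throughout, the maximum-grade table counts her as a post-baseline Grade 2, as if the grade had arisen on study. Because the table takes a maximum over all cycles, one post-baseline value at that grade is enough.

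Randomisation balances such patients between arms on average but does not remove them. They add roughly the same percentage to each arm, so both rates are too high as measures of on-study toxicity and their ratio moves toward 1.

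Safety and tolerability is a stated secondary objective. SAP 6.11 also makes optional subgroup analyses of safety endpoints depend on noticing important imbalances between arms, and a diluted contrast is harder to notice. Creatinine shows why baseline matters for this drug: "Abemaciclib has been shown to increase serum creatinine due to inhibition of renal tubular secretion of creatinine" (Protocol 10.3.3.2), while entry allows creatinine up to 1.5 × ULN.

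**Working it through.** The documents state no laboratory toxicity rate, so there is no plan figure to reproduce. What follows is an illustration.

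**Inputs**
- b, the share of each arm abnormal at baseline for an analyte: not in the documents; assumed 10% to 40%.
- p, the rate of a new abnormality among patients normal at baseline: not in the documents; assumed 60% on abemaciclib and 20% on placebo.
- w, the rate of worsening among patients abnormal at baseline: not in the documents; two cases are shown, w = 0 and w = p.
- A baseline abnormality is assumed to persist to at least one post-baseline value.

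**Formulas, any grade**
- Planned table: rate = b + (1 − b)p. Difference = (1 − b)(pA − pP).
- Counting only grades that rose above baseline: rate = bw + (1 − b)p. Difference = (1 − b)(pA − pP) + b(wA − wP).

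**Results (abemaciclib vs placebo)**

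| b | Planned table | Worsened only, w = 0 | Worsened only, w = p |
|---|---|---|---|
| 10% | 64% vs 28%; difference 36 points; ratio 2.29 | 54% vs 18%; 36 points; ratio 3.0 | 60% vs 20%; 40 points; ratio 3.0 |
| 40% | 76% vs 52%; difference 24 points; ratio 1.46 | 36% vs 12%; 24 points; ratio 3.0 | 60% vs 20%; 40 points; ratio 3.0 |

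For example, at b = 10% the planned table gives 0.10 + 0.90 × 0.60 = 0.64 and 0.10 + 0.90 × 0.20 = 0.28.

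The ratio is diluted in both cases. The difference is not: with w = 0 the two methods give the same difference. The formulas show why. The two differences are separated only by b(wA − wP), which is zero whenever worsening in the baseline-abnormal group is equal between arms.

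**Smaller effect.** With emergence of 30% versus 15% and a baseline-referenced ratio of 2.00:
- At b = 10% the planned table gives 37.0% vs 23.5%, ratio 1.57.
- At b = 30% it gives 51.0% vs 40.5%, ratio 1.26.

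**Higher grades.** For ALT, entry stops at 5 × ULN and Grade 3 starts above 5.0 × ULN. Any post-baseline ALT of Grade 3 or higher is therefore a rise from the permitted entry range, and permitted entry values add nothing to that count. The documents give no grade limits for hemoglobin or creatinine, so the same check cannot be made for them.

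**The case against.** The strongest reply is that baseline-referenced laboratory toxicity is already planned. Protocol 12.2.12 tabulates laboratory-based treatment-emergent events by maximum grade, and SAP 6.10.2 counts a pre-existing condition only if its grade increases. This stands against a reader who infers that the plan ignores baseline for laboratory toxicity altogether. It does not close the gap, for two reasons:
- Those tables hold only what investigators report as adverse events. Protocol 10.3.1 asks for clinically significant laboratory findings that lead to a diagnosis, so a calculated grade short of that need not appear.
- The list of outputs in SAP 6.10.2 does not name the separate laboratory-based tables.

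A second reply is that SAP 6.10.4 also provides a by-cycle summary, so the post-baseline maximum is not its only output. That is correct. However, the SAP does not say whether the by-cycle table includes baseline, and such a table would not link a patient's worst grade to her own starting grade.

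A third reply concerns size. A reader might infer from the illustration that the risk difference falls from 40 points to 24. The documents do not support this as a general statement, because it requires patients abnormal at entry to worsen more often on abemaciclib. For a patient who enters at Grade 2 and simply stays there, the difference is the same under either method.

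Finally, SAP 6.1 allows further exploratory analyses, so a shift table could still be produced. That permits one but commits no one to it.

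**Conclusion.** The point holds for the calculated-grade tables of SAP 6.10.4, and it is minor. Any-grade and low-grade rates are inflated in both arms by entry abnormalities that persist, and the ratio between arms is pulled toward 1. Under assumed emergence of 60% versus 20%, the ratio falls from 3.0 to 2.3 at 10% baseline prevalence and to 1.5 at 40%. Both the prevalence and the emergence rates are assumptions, so the true size is unknown.

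Dilution of the risk difference is conditional on worsening that differs by arm among patients abnormal at baseline. The creatinine effect described in the protocol makes that plausible for one analyte, but the documents do not quantify it.

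A reader might also infer that severe laboratory toxicity is understated or that the trial's efficacy conclusions are at risk. Neither is supported. Permitted entry values cannot produce ALT counts at Grade 3 or higher. The laboratory tables are descriptive, and no primary or key secondary inference depends on them.

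**What to change.** In SAP 6.10.4 add, for each graded analyte and by arm within cohort, a shift table of baseline grade by worst post-baseline grade, with a row for missing baseline. Use the SAP 6.1.2 safety baseline. Report as treatment-emergent only patients whose grade rose above baseline. The maximum-grade table may stay beside it. State also whether the laboratory-based adverse event tables of Protocol 12.2.12 are kept, since SAP 6.10.2 does not list them.

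The cost is one more standard table per analyte. No new data are needed, because Protocol Attachment 1 already schedules central hematology and chemistry at baseline.

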### **6.10.5. Vital Signs and Other Physical Findings**

Temperature, blood pressure, pulse rate, respiration rate, weight and ECOG PS will be summarized by cycle.

### **6.10.6. Electrocardiograms**

Local electrocardiograms (ECGs) will be summarized by cycle and overall. The summary by cycle will classify patients as having normal or abnormal ECG and summarize AEs identified by ECG within each cycle. The overall summary will classify patients as having an abnormal ECG at any point and summarize all AEs identified by ECG.

## **6.11. Subgroup Analyses**

Subgroup analyses of PFS will be performed for each of following potential prognostic subgroup variables for Cohort A:

- All baseline stratification factors
- Nonsteroidal aromatase inhibitor received at cycle 1 (letrozole vs. anastrozole)
- Study entry disease status (de novo metastatic vs. recurrent metastatic vs. locoregionally recurrent)
- Measurable disease at baseline (yes vs. no)
- Number of organs involved (1 vs. 2 vs. 3+)
- Age (<65 years vs. ≥65 years)
- Country (China vs. non-China)
- PgR status (positive vs. negative)
- Tumor grade (high vs. low/intermediate vs. unknown)
- Liver metastatic (yes vs. no)
- Treatment-free interval (de novo metastatic vs. <36 months vs. ≥ 36 months vs. recurrent with no adjuvant endocrine)
- Baseline ECOG PS (0 vs.1).

Subgroup analyses of PFS will be performed for each of following potential prognostic subgroup variables for Cohort B:

- All baseline stratification factors
- Measurable disease at baseline (yes vs. no)

- Number of organs involved (1 vs. 2 vs. 3+)
- Age (<65 years vs. ≥65 years)
- Country (China vs. non-China)
- PgR status (positive vs. negative)
- Tumor grade (high vs. low/intermediate vs. unknown)
- Liver metastatic (yes vs. no)
- Baseline ECOG PS (0 vs.1)
- Received prior (neo)adjuvant chemotherapy (yes vs. no)
- Received prior endocrine therapy (tamoxifen only vs. AIs only vs. both)
- Most recent endocrine therapy (AIs vs. other ET)
- Most recent endocrine therapy ((neo)adjuvant vs. locally advanced/metastatic)
- Received prior AI (yes vs. no)
- Prior lines of ET (1 line vs 2 lines vs 2+)

If a level of a factor consists of fewer than 10% of randomized patients, analysis within that level will be omitted.

Analyses will be done within subgroup and, separately, across subgroups with a test of interactions of subgroups with treatment performed. Estimated HRs and CIs for the within subgroup analyses will be presented as a forest plot along with p-values for tests of interactions between subgroup variables and treatment.

Other subgroup analyses may be performed as deemed appropriate. If any safety analyses identify important imbalances between arms, subgroup analyses of these endpoints may be performed.

## 6.12. Protocol Violations

Important protocol deviations (IPD) or protocol violations that could potentially impact data interpretation, data integrity and patient safety across the study will be identified from the clinical database and from site monitoring. Categories of IPDs will be documented in the trial issue management plan that will contain detailed criteria used to identify IPDs.

After further review, a comprehensive listing of patients with major protocol deviations among IPDs that might have significantly affected the data interpretation and integrity or patient safety will be provided. A summary of all IPDs by treatment group and overall, as well as a listing of all IPDs will also be provided.

## 6.13. Interim Analyses and Data Monitoring

An interim analysis will be conducted under the auspices of a DMC according to the specifications set forth in the protocol.

An interim analysis on Cohort A will be conducted by the DMC after approximately 119 PFS events have been observed. The interim analysis will be conducted to provide early efficacy information and could potentially result in early communication with regulatory agencies. The O'Brien Fleming alpha spending function (Lan and DeMets 1983) will be used to preserve the

overall type I error. If the analysis of PFS is significant using the p-value boundary described in Section 6.7.1.2, the DMC will be instructed to engage the SMD, who may subsequently convene an IRC to propose actions based upon the DMC's recommendation. All patients will continue follow-up for PFS until study completion, and will remain blinded for the duration of the study unless emergency unblinding (Protocol Section 9.5.2) are met. If Cohort A show early efficacy at interim, the sponsor may consider early stop, unblinding and crossover for this cohort; however, regulatory agencies will be consulted before any action is taken.

The unblinded analysis, including review of the efficacy along with the safety data, will be conducted by the DMC. Only the DMC is authorized to evaluate unblinded interim efficacy and safety analyses. Study sites will receive information about interim results ONLY if they need to know for the safety of their patients.

At the time of the interim analysis, analyses of PFS provided to the DMC will include:

- the boundary values for significance based on the exact number of observed events,
- the p-value for a stratified log rank test comparing the two treatment arms, stratified by the randomization factors,
- an estimate of the HR between the two arms based on a Cox proportional hazards model, stratified by the randomization factors, and
- a KM analysis by treatment arm.

Safety evaluation will be based, at least, on the following data reports:

- summary of patient discontinuations and reasons for discontinuation
- summary of SAEs
- Lilly Safety System reports for all patients with SAEs
- summary of TEAEs

Details pertaining to the conduct of these analyses are provided in the JPBQ DMC Charter.

If statistical significance is not declared at the interim, a final analysis of Cohort A will be conducted with about 170 PFS events.

The interim analysis of Cohort B is triggered only if statistical significance is declared at the Cohort A interim analysis. No DMC is required for the analysis of Cohort B. The analysis will provide both safety and efficacy information of Cohort B and could potentially result in early communication with regulatory agencies, including consultation of potential decisions regarding early stop, unblinding and crossover before any action is taken.

In the case of early stop and crossover for Cohort A or Cohort B after the interim analysis, Lilly will notify investigators when the crossover begins.

If patients in Cohort A continue being followed for PFS until final analysis, the final analysis of Cohort B will be conducted at the same time of Cohort A final analysis. If Cohort A stops early at interim due to efficacy, the final analysis of Cohort B may be conducted after approximately 105 PFS events have been observed in Cohort B.

